### 1.2.1.2.3 Clinical pharmacokinetics of ribociclib

The pharmacokinetics of ribociclib have been evaluated following single and repeat daily doses in the ongoing single agent, phase I study in patients with advanced solid tumors or lymphomas [[CLEE011X2101](#)]. Following oral administration of ribociclib, peak plasma concentrations (Cmax) are achieved at approximately 1-4 hours post-dose. Ribociclib plasma exposure (Cmax and AUC0-24h) demonstrates slightly over-proportional increases across the dose range tested (50 to 1200 mg). Steady-state is generally reached by Day 8 and the mean effective T1/2 based on accumulation ratio (i.e., T1/2,acc) ranged from 12.3 to 42.9 hours across the dose range tested. The mean accumulation ratio (Racc) calculated from AUC0-24h at steady-state and AUC0-24h after a single dose across the studied doses ranged from 1.35 to 3.11. At the recommended dose for future development (600 mg), steady-state plasma Cmax (n=56) ranges from 606-6170 ng/mL (geometric mean = 1790 ng/mL or 4.1  $\mu$ M), median Tmax (n=72) is 2.1 h, and AUC0-24h (n=53) ranges from 6770-90600 ng\*h/mL (geometric mean = 23600 ng\*h/mL). At this dose, inter-patient variability in Cmax and AUC is 62% and 66%, respectively, as assessed by geometric coefficient of variation (CV%). At the 600 mg dose level, LEQ803, an active metabolite of ribociclib, accounted for approximately 8% (geometric mean) of ribociclib AUC0-24h after single and multiple doses. Refer to the LEE011 (ribociclib) [Investigators Brochure] for more details. In the human ADME study [[CLEE011A2102](#)], a single oral dose of 600 mg [C]LEE011 was administered to 6 healthy male subjects. The majority of the administered dose was excreted in feces (69.1%), with a minor amount excreted in urine (22.6%). Absorption was estimated to be approximately 58.8%. Ribociclib accounted for approximately 23% of the total radioactivity in plasma, based on AUCinf. Metabolites M1 (glucuronidation of M15), M4 (LEQ803, N-demethylation) and M13 (CCI284, N-hydroxylation) were the most abundant metabolites in plasma, representing an estimated 7.78%, 8.60% and 9.39% of total [C]AUC0-48h, and 17.9%, 19.8% and 21.6% of ribociclib AUC0-48h, based on metabolite profiles. In a food effect study [[CLEE011A2111](#)] in 24 healthy subjects, a single dose of ribociclib (600 mg) was administered as drug-in-capsule (DiC) with a high-fat, high-calorie meal and under fasted conditions. Compared to the fasted state, oral administration of a single 600 mg dose of ribociclib DiC with a high-fat, high calorie meal decreased the rate of absorption resulting in a 23% decrease in Cmax (geometric mean ratio: 0.775; 90% confidence interval [CI]: 0.700, 0.858) and a median difference in Tmax of 2 hours. However, there was no effect on the extent of absorption as the overall exposure (AUCinf) was unaffected under fed conditions (geometric mean ratio: 0.994; 90% CI: 0.925, 1.070). A similar trend was observed for LEQ803, an active metabolite of ribociclib, with a decrease in Cmax (32%), a delay in median Tmax, and no substantial effect on overall exposure. Results from this study indicate the DiC can be taken without regard to meals. Refer to the LEE011 (ribociclib) [Investigators Brochure] for more details.

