## 2.3 Rationale for dose and regimen selection

The ribociclib dose and regimen selected for this study is 600 mg daily 21 days on/7 days off. In the FIH study of single agent ribociclib in adult patients with solid tumors [[CLEE011X2101](#)], the MTD of ribociclib was 900 mg QD with a 3 weeks on/1 week off schedule. The recommended dose for future development was 600 mg QD with a 3 weeks on/1 week off schedule, which showed an acceptable safety profile, low risk for QTcF prolongation, adequate exposure, and preliminary evidence of disease stabilization as single agent. In the phase III study of ribociclib/placebo (600 mg) combined with letrozole (2.5 mg once daily) in postmenopausal women with advanced breast cancer HR+ HER-2 negative [[CLEE011A2301](#)],

the DMC which took place on October 7, 2015 and reviewed safety of 664 patients, recommended to continue the study without changes.

Fulvestrant will be administered at the dose according to its approved label, 500 mg IM as two 250 mg 5 ml injections (one in each buttock) on days 1, 15, 29 and then monthly thereafter (FASLODEX® [prescribing information](#)).

Based on available data from preliminary results of patients treated with the combination of ribociclib at 600 mg and fulvestrant at 500 mg in study [\[CLEE011X2108\]](#), the combination is tolerable and a DDI between ribociclib and fulvestrant is unlikely. Therefore, these doses will also be used in this study.

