#### 6.5.1.2.2 Additional follow-up for QTcF prolongation

**Table 6-6 Ribociclib/placebo dose adjustment and management recommendation for QTcF prolongation (CTC AE v4.03)**

Grade	Dose Modification
For All Grades	
 
• 1 Check the quality of the ECG and the QT value and repeat if needed.
 
• 2 Perform analysis of serum electrolytes (K+, Ca++, Phos, Mg++). If outside of the normal range, interrupt ribociclib/placebo administration, correct with supplements or appropriate therapy as soon as possible, and repeat electrolytes until documented as normal.
 
• 3 Review concomitant medication usage for the potential to inhibit CYP3A4 and/or to prolong the QT interval.
 
• 4 Check compliance with correct dose and administration of ribociclib/placebo.
 

1* QTcF 450-480 ms	Perform steps 1-4 as directed in “For All Grades.” No dose adjustment required.

2* QTcF 481-500 ms
	
Interrupt ribociclib/placebo. Perform steps 1-4 as directed in “For All Grades.” Perform a repeat ECG within one hour of the first QTcF of <math>\geq 481</math> ms. Repeat ECG as clinically indicated until the QTcF returns to <math><481</math> ms. Restart ribociclib/placebo with dose reduced by 1 dose level. Refer to Table 6-3 for dosing schedule.. If QTcF <math>\geq 481</math> ms recurs, ribociclib should be reduced again by 1 dose level.  Repeat ECGs 7 days and 14 days after dose resumption (then as clinically indicated) for any patients who had therapy interrupted due to QTcF <math>\geq 481</math> ms.

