### **Sample size justification for PK collection**

Sparse PK sampling will be performed on approximately 150 patients ([Table 7-6](#)). Assuming a 2:1 ratio between the ribociclib and placebo arm, sparse plasma concentrations for ribociclib will be available in approximately 100 patients. Trough PK sampling will be performed in all remaining patients ([Table 7-7](#)). PK data collected from this study may also be combined with data from other studies to support a population PK analysis of ribociclib using non-linear mixed effect modeling. The choice of sampling time points was selected to ensure capture of Cmax. The aim of this analysis is to analyze the pharmacokinetics of ribociclib in a sample size as large as possible. This sample is anticipated to represent the covariate distributions in the targeted population. No specific hypothesis will be tested and therefore no specific sample size calculation has been performed. The decisions on number of sparse PK samples and number of patients needed are driven by feasibility.

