3.10.3.2 Exposure vs. QTcF

The relationship between ribociclib concentration and the mean change from baseline QTcF (i.e., Δ QTcF) will be explored graphically: the arithmetic mean Δ QTcF and geo-metric mean ribociclib concentration will be displayed together against nominal time (time in x-axis, Δ QTcF and concentration in y-axis) using the PAS. The mean will be taken with respect to all the measurements from all patients at the same given nominal time. If a patient does not have both QTcF and evaluable PK measurement at a certain time point, then this patient will not be included in the plot for that time point.

In addition, the relationship between ribociclib dose level and QTcF will also be explored using the safety set. Patients will be classified into the following dose groups at each scheduled QTcF collection time point on C1D15 and C2D15.

- RIBO600: consists of all patients who received at least 10 consecutive daily ribociclib doses of 600 mg without a dose change or interruption immediately prior to the corresponding QTcF collection timepoint.
- RIBO400: consists of all patients who received at least 10 consecutive daily ribociclib doses of 400 mg without a dose change or interruption immediately prior to the corresponding QTcF collection timepoint.
- RIBO200: consists of all patients who received at least 10 consecutive daily ribociclib doses of 200 mg without a dose change or interruption immediately prior to the corresponding QTcF collection timepoint.

Summary statistics of the raw QTcF data and change from baseline will be presented by visit, time point and dose group using the safety set. Only scheduled QTcF on C1D15 and C2D15 will be included in the analysis.

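### The ribociclib dose-level versus QTcF table compares groups formed partly by QTcF itself, so at Cycle 2 Day 15 it can understate or reverse the dose effect

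*SAP*

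**What the plan says.** The SAP for the primary PFS analysis (based on protocol Amendment 2) has two exposure displays for QTcF in section 3.10.3.2. The first plots mean change in QTcF and geometric-mean concentration together against nominal time, averaging over all patients. The second is the one at issue: "In addition, the relationship between ribociclib dose level and QTcF will also be explored using the safety set". The groups are defined visit by visit: "Patients will be classified into the following dose groups at each scheduled QTcF collection time point on C1D15 and C2D15". RIBO600, RIBO400 and RIBO200 each require at least 10 consecutive daily doses at that level, without change or interruption, immediately before the ECG. The output is plain: "Summary statistics of the raw QTcF data and change from baseline will be presented by visit, time point and dose group". There is no split by reason for reduction, no within-patient comparison, no adjustment and no caveat.

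On how patients reach the groups, protocol section 2.3 says "The ribociclib dose and regimen selected for this study is 600 mg daily 21 days on/7 days off". Tables 6-4 to 6-8 then order reductions for haematological, hepatic, QTcF and other toxicity. For QTcF of 481-500 ms the current Table 6-6 reads "Restart ribociclib/placebo with dose reduced by 1 dose level". For 501 ms or more it also lowers the dose by one level once QTcF has recovered.

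The SAP document history records that SAP Amendment 1 replaced a model-based exposure-ECG analysis with this dose-group summary.

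**The concern.** This is confounding by indication. A patient whose QTcF is prolonged at 600 mg is interrupted, so leaves RIBO600, and after restarting lower enters RIBO400. RIBO600 loses QT-sensitive patients and RIBO400 gains them. A difference between the groups then mixes the effect of dose with the tendency of those patients to have long QTcF at any dose.

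At stake is how a known risk is described. The Amendment 3 rationale says that ribociclib prolongs QT in a concentration-dependent way and that dose reduction is effective. An uncaveated table from the same trial could appear to show little benefit of a lower dose, or the opposite. The companion plot does not help, because averaging over patients by nominal time cannot recover a patient-level concentration-QTcF relation.

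**Working it through.** The plan states no expected difference or sample size for this table, so there is no figure to reproduce. Three checks follow.

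**1. Can a QTcF-driven reduction reach each visit's table?**

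- C1D15, pre-dose: RIBO400 needs 400 mg on Days 5-14 (10 doses). In the current Table 7-5a the first scheduled on-treatment ECG is C1D15 itself, so only an unscheduled earlier ECG could place a QTcF-reduced patient there. Few reductions of any kind would occur that early. The group is likely near empty. Amendment 4 updated the ECG schedule, so the schedule in force in 2015-16 is not visible.
- C2D15: prolongation at C1D15, interruption, and restart at 400 mg on C2D1 gives doses on Days 1-14. That is 14 doses, against the 10 required. The route is open.

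**2. Which rule governed these data?**

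Enrolment ended in June 2016 and the primary analysis was in January 2018. The first-occurrence reduction at 481 ms came with Amendment 3 (August 2018). Amendment 1 had already updated QTcF dose-modification guidelines, but its text is not in the documents. Both a 481 ms and a 501 ms trigger are therefore tried below.

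**3. How large could the bias be?**

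Assumptions, none given by the documents except where stated:

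- normal QTcF at 600 mg with between-patient SD 15 or 20 ms;
- correlation r between the trigger ECG and the later ECG, with (SD, r) = (15, 0.4), (15, 0.6), (20, 0.6) and (20, 0.8);
- true fall d from 600 to 400 mg of 5, 10 or 15 ms;
- P(QTcF of 481 or more) of 5% or 13.5%, the latter being the phase I Grade 2 rate at 600 mg (10 of 74, protocol 1.2.1.2.1);
- a further 10% of the remaining patients reduced for reasons unrelated to QTcF.

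This gives 4 x 3 x 2 = 24 settings per trigger. Let q be the probability of exceeding the trigger, c its standard normal cut-off, and phi the normal density.

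- Same-dose gap between triggered and other patients: G = r x SD x phi(c) / [q(1-q)].
- Share of the 400 mg group reduced for QTcF: s = q / [q + 0.1(1-q)].
- Expected table contrast, 400 minus 600 mg: s x G - d.

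Extremes:

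| Trigger | P(481 or more) | SD, r | q | phi(c)/[q(1-q)] | G (ms) | s | d (ms) | Contrast (ms) |
|---|---|---|---|---|---|---|---|---|
| 481 | 5% | 15, 0.4 | 0.050 | 2.171 | 13.0 | 0.345 | 15 | -10.5 |
| 481 | 13.5% | 20, 0.8 | 0.135 | 1.859 | 29.7 | 0.609 | 5 | +13.1 |
| 501 | 5% | 15, 0.4 | 0.0014 | 3.268 | 19.6 | 0.014 | 15 | -14.7 |
| 501 | 13.5% | 20, 0.8 | 0.0177 | 2.509 | 40.2 | 0.153 | 5 | +1.1 |

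Simulation with 2,000,000 patients per setting gave -10.5 to +13.2 ms at 481 ms, positive in 12 of 24 settings. At 501 ms it gave -14.7 to +1.2 ms, positive in 1 of 24. In all 48 settings the contrast was closer to zero than the true effect, or had the wrong sign. Among QTcF-reduced patients alone, the 400 mg mean exceeded the 600 mg mean in 46 of 48.

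These figures are for raw QTcF. The change-from-baseline column is selected too. With the current exclusion of screening QTcF above 450 ms, a value of 481 ms implies a rise of at least 481 - 450 = 31 ms from screening.

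**The case against.** The strongest reply is that little depends on this table. The SAP calls it exploratory and attaches no test or estimate. QT harm is reported by randomised arm elsewhere: section 3.9.4 gives QTcF and change by arm and time point, notable values, shift tables and time to Grade 2 or worse prolongation, and section 3.9.1.5 lists QTc prolongation as an adverse event of special interest. All of that stands. A reader might infer that the trial misreports its main cardiac harm, or that QTcF management rests on this table. The documents support neither. Amendment 3 bases the management change on the exposure-QTcF relation and on experience from three trials.

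It is also tempting to conclude that the table will probably have the wrong sign. That follows only if the 481 ms first-occurrence rule is read back onto data collected before it existed, and even then only half the settings reverse. If the earlier rule required recurrence before reduction, few QTcF-reduced patients could complete 10 doses by C2D15. Reductions for other toxicity dilute the effect further. What survives is that reversal is possible, and that some understatement appears in every setting tried.

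A third reading is that exposure overlap is itself a bias. The phase I geometric CVs of 62% (Cmax) and 66% (AUC) give log SDs of sqrt(ln(1 + 0.62^2)) = 0.57 and sqrt(ln(1 + 0.66^2)) = 0.60, against ln(600/400) = 0.41. A random 400 mg patient would then exceed a random 600 mg patient in about 31-32% of pairs. This is noise, and would occur in a randomised dose comparison too. It makes concentration the sharper scale, but does not distort group means.

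**Conclusion.** The concern holds in a limited form. At C2D15 the RIBO600/400/200 summary is partly selected on the outcome it tabulates and cannot be read as a dose effect. It can understate or reverse that effect. The size cannot be derived from the documents. The ranges above rest on assumed SDs, correlations, dose effects and reduction rates, and above all on which trigger applied. At C1D15 the likely problem is an almost empty group, subject to the ECG schedule then in force. This is a worthwhile improvement to an exploratory safety analysis. It does not touch PFS, OS or the comparison of QT events between arms.

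**What to change.** In SAP 3.10.3.2, make the exposure-QTcF analysis a linear mixed model of change from baseline in QTcF on time-matched ribociclib concentration:

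- fixed effects for baseline QTcF, treatment arm and nominal time;
- a patient random intercept, with a random slope only if the data support it;
- placebo patients included at concentration 0;
- report the slope, and the predicted change at the geometric-mean concentration with its confidence interval.

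Keep the RIBO600/400/200 summary as description only, with a footnote that the groups arise from toxicity-driven reductions and are not a dose comparison.

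No new data are needed. On the current schedules, Tables 7-5a and 7-6 pair ECG and PK at pre-dose, 2 h and 4 h on C1D15, at pre-dose on C2D1, and at pre-dose and 2 h on C2D15. Patients outside the sparse group contribute pre-dose samples. The costs are restoring model-based programming dropped in SAP Amendment 1, and limited post-dose information: "sparse plasma concentrations for ribociclib will be available in approximately 100 patients". The footnote alone would remove most of the risk of misreading, but would leave the trial without a usable exposure-QTcF estimate. Nothing here proposes or changes a dosing rule.

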3.10.3.3 Exposure vs. liver function

Box plots for ribociclib C_{trough_avg_ss} will be presented by worst post_baseline LFT lab category (for TBIL, AST, ALT, ALP separately) using the PAS set. The categories are defined as:

- TBIL (" $\leq 2x$ ULN" vs. " $>2x$ ULN"),
- AST (" $\leq 5x$ ULN" vs. " $>5x$ ULN"),
- ALT (" $\leq 5x$ ULN" vs. " $>5x$ ULN"),
- ALP (" $\leq 1.5x$ ULN" vs. " $>1.5x$ ULN")

[figure not shown]
3.10.4 Handling missing and invalid values

[figure not shown]
Plasma samples will be assayed for ribociclib concentrations by Novartis or Novartis designated laboratory using validated LC-MS/MS methods with a LLOQ of approximately 1.00 ng/mL for ribociclib.

[figure not shown]
[figure not shown]
All concentrations below the LLOQ will be displayed in listings as zero with a flag and handled as zero in any calculations of summary statistics, but handled as missing for the

[figure not shown]
calculation of the geometric means and their CV%. The number of non-zero concentrations will also be reported in the summary statistics.

Missing values for any PK data will not be imputed and will be treated as missing.

3.14 Interim analyses

3.14.1 Primary Endpoint: PFS

No Planned interim analysis for PFS.

3.14.2 Overall Survival

Overall survival will be compared between the two treatment groups, provided the primary endpoint PFS is statistically significant favoring the test treatment arm (fulvestrant + ribociclib). A hierarchical testing procedure will be adopted in this study and the treatment effect on OS will be tested only if the primary efficacy endpoint PFS is statistically significant. A maximum of 3 analyses are planned for OS: at the time of analysis for PFS (provided PFS is significant), at which point a total of 161 deaths are expected, after 263 events have been documented, and a final analysis for OS when 361 deaths are expected (expected 56 months from date of first patient to be randomized).

An α -spending function according to Lan-DeMets (O'Brien-Fleming), (as implemented in East 6.3) along with the testing strategy outlined below will be used to maintain the overall type I error probability (Lan and DeMets 1983). This guarantees the protection of the 2.5% overall level of significance across the two hypotheses and the repeated testing of the OS hypotheses in the interim and the final analysis (Glimm 2010). The trial allows for the stopping of the study for a superior OS result, provided the primary endpoint PFS has already been shown to be statistically significant favoring the test treatment arm (fulvestrant + ribociclib). Further, the exact nominal p-values that will need to be observed to declare statistical significance at the time of these analyses for OS will depend on the number of OS events that have been observed at the time of these analyses and the α for OS already spent at the time of earlier analyses.

The operating characteristics for OS are shown in Table 3-9 considering the hierarchical testing strategy of PFS and OS. The probabilities shown in Table 3-9 are conditional on PFS being statistically significant.

Statistical properties of the group sequential design are summarized in Table 3-9.

[figure not shown]
Table 3-9 Projected timelines for interim and final analyses

[figure not shown]
Months after randomization of the first patient	PFS events	Cumulative Power (%) against a hazard ratio of 0.67	OS events	Cumulative Conditional Power (%) against hazard ratio of 0.71
26	364 (100%)	95	161(46%)	14
39	--	--	263(75%)	60
56	--	--	351(100%)	85

Statistical significance of OS will only be declared if significance for primary PFS analysis has been declared.

3.14.3 Confidentiality of Interim OS results

At the time of primary PFS analysis, both PFS and interim OS analysis will be performed by the Sponsor's clinical team. Investigators and patients will remain blinded to study treatment and all patients will continue to be followed for OS until the final OS analysis (or earlier if OS reaches statistical significance at any of the interim analyses).

3.16 Sample size calculation

The median time to progression (TTP) for fulvestrant in first line post-menopausal advanced breast cancer patients is estimated to be between 8 month ([Howell 2004](#)) and 23 months in FIRST trial ([Robertson et al 2012](#)). For sample size calculation, the median PFS for 1st line patients is assumed to be 18 month. The median PFS for fulvestrant in relapsed advanced breast cancer is estimated to be between 4.8 months (SoFEA trial, [Johnston et al 2013](#)) and 6.5 months (CONFIRM trial, [Di Leo et al 2010](#)). Since the study population is closer to the population in CONFIRM trial, for sample size calculation, the median PFS for fulvestrant in second line is assumed to be 6.5 months. It is assumed that 40% and 60% of the patients will

be from first line and second line respectively. The median PFS in the control arm (fulvestrant + placebo) is estimated via simulation to be around 9 months. It is hypothesized that the addition of ribociclib will result in a clinically meaningful 33% reduction in the hazard rate of PFS, corresponding to an increase in median PFS to 13.4 months. A maximum of 364 PFS events will be required to detect a hazard ratio of 0.67 with 95% power using the log-rank test at one-sided cumulative 2.5% level of significance. Assuming that enrollment will continue for approximately 19 months at a uniform rate and 10% dropout rate by the time of PFS final analysis, a total of 660 patients should be randomized to the two treatment groups in 2:1 ratio to observe 364 events at approximately 7 months following the randomization of the last patient, i.e., 26 months from the randomization date of the first patient in this study. The sample size calculation was conducted with software package East 6.3. The sample size calculations are based on the estimates from data available from prior studies. A mid-study sample size re-assessment based on blinded pooled data may be performed prior to any efficacy analysis if data from the study indicate substantial deviation from the study assumptions.

The primary objective of the study is to compare investigator assessed PFS between arms in the overall population (both 1st line and 2nd line patients). If the primary analysis is statistically significant, treatment effect will be evaluated in 1st and 2nd line patients (i.e. previous endocrine therapy stratification factor A and B as defined in section 1.1) separately. Based on the estimated median PFS and proportion of patients in 1st line and 2nd line respectively, it is expected that the accumulation of events in 1st line will be slower than 2nd line patients. To ensure enough information coming from 1st line patients, the final analysis will be done after approximately 125 events in the first line patients or approximately 364 events in both arms whichever comes later.

Audit size for BIRC assessed PFS

The audit size of the sample-based BIRC assessment will be 40% of all randomized patients. Based on the audit size calculation approach proposed by Dodd, et. al (2011), assuming investigator and BIRC assessments are similar and the estimated log of investigator-based HR is -0.40 (i.e., HR=0.67), the audit size of 40% will ensure that the upper bound of a one-sided 95% CI for BIRC-based log-hazard ratio has 86% probability of being below 0 (i.e. HR < 1) if the correlation between investigator assessment and BIRC assessment is 0.7 (the estimated correlation based on data from the BELLE-2 [CBKM120F2302] study in metastatic breast cancer).

